The CP288 Coloplast investigational products are non-CE marked stoma products based on the [REDACTED] and a [REDACTED] products to which comprises of a [REDACTED]. The comparator products are considered Standard of Care or products considered to be part of Standard of Care in coming years, and include:

1-piece

2-piece

They are considered the newest products launched by the largest manufacturers covering the majority of the market.

Intended purpose

The product is intended to support collection of output from a stoma and to provide a [REDACTED] between peristomal skin and stoma output.

Aim and objective(s)

The **aim** of this investigation is to investigate the performance and safety of a new baseplate [REDACTED] which is expected to reduce peristomal skin complications induced by output.

The **primary objective** is to investigate whether a new baseplate with a [REDACTED]

The **secondary objective** is to evaluate the [REDACTED] for the peristomal skin condition.

Design of the investigation

This investigation is a randomised, controlled, open-label, comparative, cross-over, multicentre investigation, with two test periods. In total, 96 subjects will be included and randomised, and each subject will have three test visits overseen by the Principal Investigator, or delegate. Each subject will be enrolled for $2 \times 42^{\pm 3}$ days in total for the entire investigation, thus for a maximum of 90 days. The subjects will test the non-CE marked Investigational product and one of the five comparator investigational products in randomised order.

Expected duration of the clinical investigation:

The investigation will be conducted in January 2020 through May 2020.

Primary endpoint

- Max itching score within a week at steady state

For Secondary and explorative endpoints please see Appendix 1 - Endpoints.

.

CONFIDENTIAL

Population/subjects

Subjects with an ileostomy or colostomy with liquid output, currently using a flat (e.g. non-convex/concave) baseplate.

To take a potential drop-out (20%) into account it is recommended to include a total of 48 1-piece and 48 2-piece users, resulting in a total of 96 subjects included and randomised.

The subjects will be included by competitive recruitment in up to 15 sites in five different countries (UK, Germany, the Netherlands, Italy and Norway).

Investigation approval

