5.2. Comparator investigational product(s)

The following comparator products has been chosen for this investigation:

1P:

A series of five horizontal black redaction bars of varying lengths, representing a list of 1P comparator products.

2P:

A series of five horizontal black redaction bars of varying lengths, representing a list of 2P comparator products.

The comparator investigational products are considered Standard of Care or products considered to be part of Standard of Care in coming years, and therefore the newest products launched by biggest manufacturers covering the majority of the market.

The comparator products are already on the market and will be used within the intended purpose in this clinical investigation.

CONFIDENTIAL

6. Clinical Investigation population

Based on the sample size calculation (see section 11.2) 48 1-piece and 48 2-piece users should be included and randomised.

The subjects will be included by competitive recruitment in up to 15 sites in five different countries (UK, Germany, the Netherlands, Italy and Norway).

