Subject Information Form	
If subjects are eligible and interested in participating, then written information about the investigation (subject information) will be sent to the subjects to ensure that they are given the opportunity to read about the investigation before a possible informational visit, and for them to prepare any possible questions they may have. The subject information provides information to subjects about how to contact the investigator or a representative thereof, or a representative of the sponsor (name, telephone number and e-mail address), if they wish to learn more about the study.
		
First visit Information visit	
If an eligible subject is interested in participating after the first contact, a visit will be arranged in a room reserved to ensure privacy and quiet surroundings at the investigators clinic/department. When arranging the visit, it will be ensured, that the subject has received the Information Form prior to the visit. The subjects will receive both written and verbal information about the possibility of bringing a companion to the informational visit and to any possible subsequent visits.
 
See section 13 for information to be given to the subjects, as well as the informed consent process.
		
Enrolment and inclusion visit (V0)	
The subjects have the right to wait before deciding on participation. If/when the subject decides to participate, he/she will be asked to sign the relevant forms (see section 13). If a subject so desires, and it is certain that it is understood what the investigation entails, and the relevant forms have been signed the subjects are considered enrolled in the investigation.
		

The coordinating clinical manager will have close contact to each site during the recruitment period. The principal investigator, or delegate, at each site will notify the clinical manager of all planned inclusion visits and whenever a subject is enrolled.

When either 48 1-piece or 2-piece users have been included, the inclusion of the respective group, will be paused, to aim for 48 1-piece users and 48 2-piece users to be included.

When the coordinating clinical manager is aware that 96 subjects have been included and randomised, the recruitment will stop. Subjects who have been informed of the investigation and are reflecting on their participation may be included within the first 24 hours hereafter.

CONFIDENTIAL

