6.3.1. Screening failures

Screening failures are considered subjects that have signed the informed consent form and been included based on in- and exclusion criteria, but not yet randomised.

Subjects that have signed the informed consent form but fails to comply with the in- and exclusion criteria are also considered screening failures.

Screening failures can be replaced by a new subject.

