11.1. Statistical design, method and analytical procedures

The primary objective will be evaluated by analysing the primary and secondary endpoints. These analyses are carried out by Medical Affairs, Coloplast A/S and are described in the following. The secondary objective regarding the [REDACTED] will be evaluated out by [REDACTED] and [REDACTED]

All baseline measurements, endpoints and other measurements (see Appendix 1 - Endpoints) will be summarized by descriptive statistics and/or listed. Endpoints and other measurements will be summarized by product, product type (1- or 2-pc) and visit, if relevant. Descriptive statistics for continuous variables are presented with N, Mean, SD (standard deviation), Median, Min and Max), where N denotes the number of subjects contributing with non-missing data. For discrete variables, descriptive statistics are presented with N and percentage, where percentage is based on the total number of subjects/observations with non-missing data.

As it is an exploratory study no adjustment for multiple testing will be applied.

All statistical analyses are made with SAS version 9.4 (SAS Institute Inc., Cary, NC)

Definition of analysis populations

Intention to Treat (ITT), Safety and Per Protocol (PP) populations will be defined at a formal data review meeting just before database lock. As a minimum, the data manager, the clinical manager and the statistician will be involved in the classification of subjects.

The ITT population (full analysis set) will be constituted by all randomised subjects with valid informed consent who have been exposed to at least one product, and with valid information on at least one product with respect to either primary or secondary endpoints.

The PP population will be constituted by a subset of ITT subjects who fulfilled the inclusion/exclusion criteria and did not violate the protocol in a serious way

Any exclusion of subjects from the PP/ITT population must be documented. Invalid individual data points may be omitted from analysis even though the corresponding subject is part of the ITT or PP population. Any exclusion of data points will be documented.

The Safety population will constitute by subjects who have given informed consent.

All statistical analysis will be based upon the ITT and PP population whereas adverse events and Device deficiencies will be assessed based on the safety population.

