11.2. Sample size

The itching score is given at each baseplate change and the max of these scores per week at steady state is the primary endpoint. The max score is only calculated if there are measurement for more than four days within a week. For each subject approximately three measurements will be available for each test period.

The sample size calculation is based on a simplified linear mixed model with only 1-pc users and no period effect (corresponding to the design from CP300). The model includes a fixed effect of product (comparator and test product), a random effect of subject and a random interaction effect of product and subject.

Based on data from CP300 it is assumed that the total standard deviation of the primary endpoint is 1.82 and that the total variation 1.82² is divided so that:

- a random effect of subject accounts for 68% of the total variation
- a random interaction effect of product and subject accounts for 0%
- and the residual accounts for 32% of the total variation

In table 1 the needed sample size is calculated by simulation for varying values of the true difference between comparator and test product regarding mean max itching score per week and for different values of the power to demonstrate that the difference is significantly different from 0.

Table 4: Subjects needed for comparing mean max itching score between two products

True difference	Reduction in mean if the mean for the comparator is 2.2 as for [REDACTED] in CP300	Power		
		0.8	0.85	0.9
0.6	27%	46	>46	>46
0.7	32%	35	40	45
0.8	36%	30	32	36

Based on the numbers in the table, 40 subjects should test each product to ensure a power of 85%, if the true difference between the comparator product and a test product is 0.7 (corresponding to a 32% reduction if the mean for the comparator is 2.2 as in CP300). This will be enough when comparing the two products. 1-pc and 2-pc users will be evaluated separately (in a combined model). As there are no previous data for 2-pc users the sample size calculations for 1-pc users is assumed to cover 2-pc users as well. To take a potential drop-out (20%) into account it is recommended to include a total of 48 1-pc and 48 2-pc users, resulting in a total of 96 subjects.

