If a carry-over effect is present and therefore data from only the first period is analysed as a parallel arm trial 40 subjects (20 in each arm) will ensure a power of 82% if the true difference between the comparator product and the test product is 1.7. If there are no significant difference between 1- and 2-pc users, 80 subjects (40 in each arm) will ensure a power of 83% if the true difference between the comparator product and the test product is 1.2 (the difference in CP300 was estimated to 1.3).

The total number of 80 subjects is the required number of subjects for the [REDACTED]

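### The target of 48 per product type covers a drop-out of 16.7%, not the stated 20%; the effect on power is small

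*Combined protocol and SAP*

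**What the plan says.** Section 11.2 sets the evaluable number for a true difference of 0.7: "40 subjects should test each product to ensure a power of 85" percent. It evaluates 1-piece and 2-piece users separately within one model and carries the 1-piece calculation over to 2-piece users, so 40 is needed in each type. It then moves to the recruitment target: "To take a potential drop-out (20%) into account it is recommended to include a total of 48 1-pc and 48 2-pc users", which makes 96.

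The synopsis repeats the claim: "To take a potential drop-out (20%) into account it is recommended to include a total of 48 1-piece and 48 2-piece users". Section 6 relies on it: "Based on the sample size calculation (see section 11.2) 48 1-piece and 48 2-piece users should be included and randomised".

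Other provisions bear on attrition:

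- Section 6.2: "When the coordinating clinical manager is aware that 96 subjects have been included and randomised, the recruitment will stop". The only exception is a 24-hour allowance for people still considering participation.
- Section 6.3.1: "Screening failures can be replaced by a new subject". No replacement is described for randomised subjects who leave.
- Section 4.1 lets a subject who cannot or will not finish one test period go on to the next.
- Section 11.1 admits subjects to the ITT set "with valid information on at least one product with respect to either primary or secondary endpoints".

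Section 11.2 also names an overall figure: "The total number of 80 subjects is the required number of subjects for the", after which the text is redacted.

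**The concern.** A drop-out rate is ordinarily a share of the subjects who enter. On that reading, keeping 40 after a 20% loss means dividing by 0.8. The plan's 48 is what results from adding 20% to 40. The plan gives no formula, so the multiplication by 1.2 is inferred, but it matches exactly.

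The stated margin is part of the justification for the sample size, and ethics committees and regulators will read it as such. A sponsor who monitors attrition against 20% would think the target safe after completers had already fallen below 40 per type.

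**Working it through.** **Inputs, all from section 11.2 unless noted.** 40 evaluable per type; drop-out 20%; 48 per type and 96 in total; difference 0.7; total SD 1.82; residual share 32%; product-by-subject share 0%; significance level 5% (section 11.3). I take the test as two-sided, since section 11.2 seeks a difference from zero.

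**1. Reproduce the 48.** 40 × (1 + 0.20) = 48, an exact match. The usual formula gives 40/(1 − 0.20) = 50, or 100 in total.

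**2. Drop-out that 48 covers.** 1 − 40/48 = 16.7%. For the totals, 1 − 80/96 = 16.7%.

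**3. Subjects left to complete both periods.**

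| Drop-out | Per type (48 × (1 − d)) | Total (96 × (1 − d)) |
|---|---|---|
| 10% | 43.2 | 86.4 |
| 15% | 40.8 | 81.6 |
| 16.7% | 40 | 80 |
| 20% | 38.4 | 76.8 |

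The shortfall at 20% is 40 − 38.4 = 1.6 per type.

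**4. Effect on power, from the plan's own table.** At a difference of 0.7, Table 4 gives 35 subjects for 80% and 40 for 85%. The value 38 lies between.

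**5. Effect on power, computed.** The residual variance is 0.32 × 1.82² = 1.06. With one score per product, a subject's product difference has variance 2 × 1.06 = 2.12. The noncentrality is 0.7/√(2.12/n), which is 3.04 at n = 40 and 2.96 at n = 38. The paired t-test gives:

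| n | Computed power | Table 4 |
|---|---|---|
| 35 | 78.9% | 80% |
| 38 | 82.3% | not listed |
| 40 | 84.3% | 85% |
| 45 | 88.4% | 90% |

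This basis tracks Table 4 to within about 2 points. On it, going from 40 to 38 costs 84.3 − 82.3 = 2.0 points.

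**6. Dependence on the basis.** Section 11.2 also says that about three weekly scores are available per period. With three scores and 0% product-by-subject variance, power exceeds 99% at both 38 and 40. The 82.3% is therefore a reconstruction and should not be written into the plan.

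**7. First-period fallback (two-sample t-test, one value per subject, SD 1.82).** The plan's 82% (20 per arm, difference 1.7) reproduces as 82.1% and becomes 80.0% at 19 per arm. Its 83% (40 per arm, difference 1.2) reproduces as 83.0% and becomes 81.0% at 38 per arm. Subjects lost only after period 1 still count here, so these are the losses if every drop-out comes before first-period data are obtained.

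**The case against.** The strongest reply is that a drop-out is not always lost. Section 4.1 lets a subject leave one period and enter the next, the ITT set accepts data on one product, and the mixed model uses such data.

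A favourable case shows how far this goes. Suppose all 9.6 drop-outs per type contribute one period, split equally between products, with one score per product.

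- Information from 38.4 complete pairs: 38.4/2.12 = 18.11.
- Information from the one-period subjects, total variance 1.82² = 3.3124: 4.8/(2 × 3.3124) = 0.72.
- Sum: about 18.84, worth 18.84 × 2.12 = 39.9 complete subjects.

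Each one-period subject adds little, but together they could recover nearly all of the 1.6. By the normal approximation, with 38 complete and 10 one-period subjects, power is 85.7%, against 86.0% for 40 complete subjects and 84.2% for 38 alone. This stands as a limit on the size of the effect. It does not make 48 × 0.8 equal to 40, and subjects who leave without steady-state data add nothing.

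Two smaller points also have some force. The plan does not define the base of its 20%, so the sponsor may have meant a 20% add-on; the text ties the figure to drop-out, however, and would need rewording on that reading too. The purpose of the 80 in section 11.2 is redacted, so it is unknown whether it means completers. The finding rests on the 40 per type, and the comparison of 77 with 80 is only indicative.

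**Conclusion.** The concern holds and is minor. Taking drop-out as a share of those randomised, 48 per type protects the required 40 against a loss of 16.7%, not 20%. At 20% about 38 per type would complete both periods.

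On the one-score basis that approximates Table 4, the cost at a difference of 0.7 runs from almost nothing (every drop-out supplies one period) to about 2 points (none does). On the three-score basis that the text describes, it is negligible. The wrong figure is the stated tolerance. The design, the analysis and the recruitment target are not undermined.

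**What to change.** Replace the drop-out sentence in the synopsis and in section 11.2 with wording such as:

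> 48 1-pc and 48 2-pc users (96 in total) allow for a drop-out of about 16.7%. A 20% drop-out would leave about 38 per type (77 in total) completing both periods; for a difference of 0.7 the power then lies between the 80% (35 subjects) and 85% (40 subjects) entries of Table 4.

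Section 6 already refers to section 11.2 and needs only to stay consistent with it. The cost is one corrected sentence in two places and a stated tolerance that drops from 20% to 16.7%. Recruitment, design and analysis are unchanged. Keeping the 20% claim instead would mean recruiting 50 + 50 = 100, four more subjects, which the small effect on power does not require.

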11.3. Level of significance and power

A significance level of 5% will be applied. For a description of the power see section 11.2 above.

CONFIDENTIAL

11.4. Pass/fail criteria

The purpose of the investigation is fulfilled if a significant difference in one of the skin endpoints is estimated.

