4.4.1. Primary endpoint

- Maximum itching score within one week at steady state

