4.4.3. Rationale for the selection of endpoints

The skin endpoints are subjective and objective parameters describing the health of the peristomal skin. Therefore, these are essential to investigate if the new baseplate [REDACTED] can reduce peristomal skin complications induced by output.

[REDACTED] the baseplate and the possible effect [REDACTED] could affect feeling of security, leakage, handling, wear time and quality of life and are reasons why associated exploratory endpoints are assessed in this investigation.

Adverse events and device deficiencies comprise safety parameters.

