In light of the data obtained it might be considered to make additional explorative analyses based on a subset of the ITT/PP population.

Analysis of the primary endpoint

Max itching score within a week at steady state will be analysed by a mixed repeated measures model using individual week max scores (on a scale from 0-10) as the observational unit. The model will consider that observations corresponding to different subjects are independent; whereas observations corresponding to the same subject are correlated. The correlation between observations corresponding to the same product can be larger than observations corresponding to different products. Hence the model includes a fixed effect of product (comparator product, test product), a fixed effect of product type (1- or 2-pc), a fixed interaction between product and product type, a fixed period effect, an interaction between period and product, a random effect of subject and a random interaction effect of product and subject.

The model might be reduced by removing non-significant fixed effects, if relevant. The interaction between period and product allows for a possible carry-over effect. It is assumed that a possible carry-over effect is the

CONFIDENTIAL

same for 1- and 2-pc users. If the interaction is significant, data from only the first test period will be analysed as a parallel arm study because the first period is free of carry-over effects and period will be excluded from the model.

All combinations of differences between the two products will be estimated for both 1- and 2- pc products. Furthermore, differences for same product between product types will be estimated (if the model is not reduced).

Analysis of the secondary endpoints

The endpoints regarding pain, burning, physical discomfort, ability to move around and the overall ability to stick the baseplate to the skin (on a scale from 0-10) will be analysed by the same model as the primary endpoint starting by calculating the max within a week at steady state.

[REDACTED] endpoints regarding bleeding (Y/N), experiencing any weeping or moisture (Y/N) and Ulcers or sores (Y/N) per baseplate change at steady state will be analysed by a repeated logistic regression model with the same effects included as for the primary endpoint.

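### The pass rule in section 11.4 can be met by any one skin endpoint, so the trial can pass while its primary endpoint shows nothing

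*Combined protocol and SAP*

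**What the plan says.** Section 11.4, in full: "The purpose of the investigation is fulfilled if a significant difference in one of the skin endpoints is estimated". There is no other success criterion.

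Section 4.4.1 lists a single primary endpoint: "Maximum itching score within one week at steady state". It is also the only endpoint with a displayed sample-size calculation in section 11.2 (40 per product type, 85% power at a difference of 0.7).

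The phrase *skin endpoints* refers to a group. Section 4.4.3 says: "The skin endpoints are subjective and objective parameters describing the health of the peristomal skin". Section 11.1 then assesses the primary objective on the whole group, "The primary objective will be evaluated by analysing the primary and secondary endpoints", and adds: "As it is an exploratory study no adjustment for multiple testing will be applied". On populations it says: "All statistical analysis will be based upon the ITT and PP population".

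Section 11.3 sets the significance level at 5%. No section requires the itching result to be significant, orders the tests, or says which population or product type decides.

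**The concern.** A primary endpoint is normally the result on which a trial's claim stands or falls. Here it is one of many routes to a pass. A report that follows 11.4 exactly could declare the purpose fulfilled on one chance finding among the secondary endpoints while maximum itching shows no difference. The 85% power in 11.2 therefore describes a test that the pass rule does not require.

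The plan promises no error rate for the pass rule. But a verdict under a pass/fail heading, directly after a section setting a 5% level, is easily read as the outcome of a 5% test.

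There is also a smaller wording gap. The objective in section 3 is a reduction in complications, but 11.4 asks only for a difference, without direction.

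**Working it through.** **1. The plan's own sizing.** Inputs from 11.2: total SD 1.82, residual share 32%, product-by-subject share 0%, difference 0.7, n = 40, level 5% (two-sided, inferred from the wording of 11.2).

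- Residual variance = 0.32 × 1.82² = 1.06.
- With one value per product, the SD of the within-subject difference = √(2 × 1.06) = 1.456.
- Noncentrality = 0.7 / (1.456/√40) = 3.04. Noncentral-t power is 84%, against the stated 85%.
- First-period fallback, SD 1.82: 20 per arm at 1.7 gives 82%; 40 per arm at 1.2 gives 83%. Both match 11.2.

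So the displayed sizing is a calculation for the itching endpoint only.

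**2. How many skin analyses can trigger a pass.** From the prose of 11.1:

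| Group | Number |
|---|---|
| Weekly maximum scores (itching, pain, burning, discomfort, moving around, adhesion) | 6 |
| Yes/no signs (bleeding, weeping, ulcers) | 3 |
| Total DET score | 1 |
| Discoloration area, intensity | 2 |
| 14-day frequencies (itching, pain, burning) | 3 |
| **Firm total** | **15** |
| DET item scores, optional | 3 |
| **With optional items** | **18** |

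If moving around and adhesion are not counted as skin health, the range is 13 to 16. Some secondary endpoints are redacted and parts of Appendix 1 are lost, so the true count may differ.

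**3. Chance that an ineffective product passes in its own favour.** Assume k standard normal test statistics with common correlation ρ, one comparison per endpoint, and a pass if any z > 1.96:

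P(pass) = 1 − ∫ φ(g) · Φ[(1.96 − √ρ·g)/√(1−ρ)]^k dg

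For ρ = 0 this is 1 − 0.975^k. The documents give no correlations, so ρ is an assumption shown as a range. ρ = 0 serves as an upper limit because the endpoints overlap.

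| ρ | k = 13 | k = 15 | k = 16 | k = 18 |
|---|---|---|---|---|
| 0.9 | 6.9% | 7.2% | 7.3% | 7.6% |
| 0.8 | 9.6% | 10.1% | 10.4% | 10.8% |
| 0.5 | 16.7% | 18.1% | 18.8% | 19.9% |
| 0 | 28.1% | 31.6% | 33.3% | 36.6% |

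For the primary endpoint alone the figure is 2.5%. A simulation at k = 18 with 200,000 replicates gave 7.5%, 10.8% and 20.0% at ρ = 0.9, 0.8 and 0.5.

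**4. Favourable passes without a favourable primary.** This is P(pass) − 2.5%, for k = 15 to 18:

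| ρ | Probability | Share of all false favourable passes |
|---|---|---|
| 0.9 | 4.7–5.1% | 65–67% |
| 0.8 | 7.6–8.3% | 75–77% |
| 0.5 | 15.6–17.4% | 86–87% |

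**5. The rule read literally.** Section 11.4 states no direction. Counting a difference either way, 15 endpoints give 14.4% at ρ = 0.9, 36.1% at 0.5 and 1 − 0.95¹⁵ = 53.7% at 0. If the 1-piece and 2-piece results can each trigger a pass, these become 26.7%, 59.2% and 78.5%. The favourable-only figures in step 3 are therefore the cautious ones.

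**The case against.** The strongest defence is that the rule is consistent with a disclosed design. Section 11.1 calls the study exploratory, disclaims multiplicity adjustment, and judges the primary objective on primary and secondary endpoints together. Section 11.4 applies the same choice, so no two sections contradict each other and no 5% rate is promised. This stands as a defence of unadjusted secondary p-values, each read for what it is. It does not carry over to 11.4, which combines all those tests into one yes/no verdict.

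Itching is itself a skin endpoint, so meeting it also gives a pass. That is true, but it is not required.

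The report must evaluate all data critically (section 20), and negative results will be published (section 21). A null primary result would therefore be visible. That limits the harm but does not change the verdict that 11.4 permits.

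Section 3 and the reduction column in the sample-size table imply a direction, so the missing direction is a minor point.

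The size rests on assumptions. Correlations are unknown, a single common value is a simplification, and the endpoint count comes from partly redacted text. Twenty endpoints would give only 7.8% at ρ = 0.9 and 21% at 0.5. Section 11.2 also gives a redacted second reason for 80 subjects, so itching may not be the only driver of the sample size. None of this affects the reading of 11.4.

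**Conclusion.** The concern holds: the decision rule in 11.4 is wrong as written, and should be fixed. That follows from the text alone. The size depends on the assumed correlation and on the count of 15 to 18 analyses. The chance of a false favourable pass is about three times the primary-only 2.5% at correlation 0.9 and about seven to eight times at 0.5. At either value, most such passes would come without the primary endpoint.

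**What to change.** Reword 11.4, for example:

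> Success requires a statistically significant reduction in the primary endpoint (weekly maximum itching at steady state) on the test product compared with the comparator, in the ITT population.

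The same section should then state:

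- **Which comparison decides:** the combined product effect, or separate 1-piece and 2-piece effects. Otherwise the data-driven reduction in 11.1 ("The model might be reduced by removing non-significant fixed effects, if relevant") could choose it. If the types are separate, say whether one is enough. Adjustment across the two types, such as Holm, is optional.
- **How the rest is used:** other skin endpoints and PP results as supportive, with confidence intervals, or a named list tested in fixed sequence after the primary.

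If the sponsor keeps the any-endpoint rule, 11.4 should be labelled exploratory and should say that a pass carries no 5% error rate.

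**Cost.** This is a change of wording, and a pass becomes harder to reach.

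- *One deciding comparison at 5%:* the sizing of 40 per type is unchanged. Choosing the combined effect keeps the pooled first-period fallback (83% at 1.2) but can hide a difference between types.
- *Either type may decide, unadjusted:* the chance of a false favourable pass is 1 − 0.975² = 4.9%.
- *Optional adjustment at 2.5% per type:* the stated 85% falls to Φ(1.960 + 1.036 − 2.241) = about 77%, or about 83% with Holm if both effects are real.
- *First-period fallback by type, SD 1.82:* at 1.7, power is 82% at the 5% level and 73% at 2.5%. At 1.2 it is 53% and 41%.

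These losses may be overstated. Section 11.2 expects about three weekly values per period. With the stated variances, crossover power at n = 40 then exceeds 99% at either level. In the fallback, the SD of a three-value mean is 1.82 × √(0.68 + 0.32/3) = 1.61, which gives about 90% and 84% at 1.7, and 63% and 51% at 1.2.

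The rewording does not settle the carry-over switch in 11.1 ("If the interaction is significant, data from only the first test period will be analysed as a parallel arm study"). The choice of analysis still depends on a preliminary test, so the 5% level remains nominal.
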